4.3 Other Endpoints

Clinical efficacy of subsequent treatment (categories: complete response, partial response, stable disease, progression, unknown)

- Percentage of subjects applicable to each category of clinical efficacy by each type of subsequent treatment
- Percentage of subjects applicable to each category of clinical efficacy by each treatment line

Time to start of chemotherapy

Defined as time from the date of the first dose of the investigational product in J-Ph2 to the date of the first subsequent chemotherapy or any-cause death, whichever occurred first. Surviving subjects who had not started subsequent chemotherapy will be censored at the last date of confirmed survival.

Dose Adjustment of Palbociclib

- Percentage of subjects by types of dose reduction (category: no dose reduction, dose reduction by 1 level to 100 mg, dose reduction by 2 levels to 75 mg, others)
- Percentage of subjects by reasons for dose reduction (category: adverse event, others) among those who reduced doses

Duration of Treatment with Palbociclib + Letrozole

The duration of treatment with palbociclib per dose (category: 125 mg, 100 mg, 75 mg, etc.) is defined as time from the date of the first dose to the end of treatment with the dose level.

The duration of treatment with letrozole is defined as time from the date of the first dose per investigational product in J-Ph2 to the date of the last dose of letrozole.

4.4 Key Baseline Variables

J-Ph2 database will be used for the following classification.

- ECOG PS
- Disease Free Interval since completion of prior therapy
- Prior Adjuvant Anticancer Treatment
- Disease Site (visceral, non-visceral)
- Disease Site (bone only, other)
- Age (<65, >=65)
- Dose Reduction Group
- Prior Chemotherapy
- Prior Endocrine Therapy
- Ki67 Status (<=20%, >20%)

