9.3. Variables

The same patient IDs will be used for this study and J-Ph2. Data collected in this study will be combined and evaluated with J-Ph2 data, including patient demographics, study treatment, and baseline tumor assessment, through matching with patient IDs. Variables and data sources are described in Table 1. Detailed definitions will be included in the statistical analysis plan (SAP).

Table 1. Variables in this study

Variable	Role	Data source(s)
Overall Survival	Outcome	J-Ph2 database A5481154 database
Type of subsequent therapy	Outcome	J-Ph2 database A5481154 database
Duration of subsequent therapy	Outcome	J-Ph2 database A5481154 database
Clinical response of subsequent therapy	Outcome	A5481154 database
Palbociclib dose modification	Exposure, Outcome	J-Ph2 database A5481154 database
Palbociclib treatment duration	Exposure, Outcome	J-Ph2 database A5481154 database
Letrozole treatment duration	Exposure, Outcome	J-Ph2 database A5481154 database
Demographic and baseline characteristics	Baseline characteristics	J-Ph2 database

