9.4. Data sources

9.4.1. Data to be collected in this study

Data to be collected in this study is described in Table 2. See Section 9.4.2 and 9.4.3 for data collection time point and data collection methods.

Table 2. Data to be collected in this study

CRF	Variables
Informed consent	Patient status at study initiation ⁴
	Informed consent obtained
	Date of informed consent
Survival status	Survival status
	Date last known to be alive
	Date of death
	Cause of death
Subsequent therapy	Drug name of subsequent therapy
	Start and Stop date of subsequent therapy
	Clinical response of subsequent therapy ¹
PAL+LET exposure	Total daily dose ²
	Start and Stop date of each dose ³
	Reason for dose change ²
PAL+LET discontinuation	Date of treatment discontinuation ³
	Reason for treatment discontinuation ³
	Disease site and tumor assessment at treatment discontinuation

Abbreviation; LET=letrozole, PAL=palbociclib

1. Clinical response of subsequent therapy will be evaluated with Complete response, Partial response, Stable disease, Progression disease, and Unknown. See Section 9.4.1.1. for detail.
2. Palbociclib only
3. Data will be collected for palbociclib and letrozole, respectively
4. Patient status at study initiation will be collected as alive and has routine site visit, alive and had transferred to another hospital, dead

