4 DEFINITIONS OF ENDPOINTS AND BASELINE VARIABLES

4.1 Primary Endpoint

Overall survival (OS)

Defined as time from the date of the first dose of the investigational product in J-Ph2 to the date of any-cause death. Subjects whose death was unconfirmed will be censored at the last date of confirmed survival.

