7.4 Subgroup Analyses

The same analysis described in "7.1 Primary Endpoint" will be performed for each category shown in "4.4 Major Baseline Variables" and for each category of the duration of palbociclib treatment (threshold: median, 24 months).

The following subgroup analyses will be performed based on the Kaplan-Meier method used for the Subsequent-treatment period (First Line) specified in 7.2 "Secondary Endpoints."

- Types of First Line
- Disease Site (visceral, non-visceral)

Plots for each subject in the subsequent-treatment period as per 7.2 "Secondary Endpoints" will be used to perform the following subgroup analyses.

- Disease Free Interval since completion of prior therapy
- Disease Site (visceral, non-visceral)
- Duration of treatment with palbociclib (threshold, median, 24 months)

The following subgroup analyses will be performed based on the Kaplan-Meier analyses for time to start of chemotherapy specified in 7.3 "Other Endpoints."

- Disease Free Interval since completion of prior therapy

- Disease Site (visceral, non-visceral)

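### Dose Reduction Group is a post-baseline event used as a baseline subgroup for OS from first dose, which builds immortal time into the reduced group

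*SAP*

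**What the plan says.** SAP 4.4 (Key Baseline Variables) opens with "J-Ph2 database will be used for the following classification" and includes "Dose Reduction Group" in the list. Age and Ki67 get cut-points there. Dose Reduction Group gets no categories and no date at which status is fixed.

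SAP 7.4 states that the primary-endpoint analysis "will be performed for each category shown in" the list in 4.4, and also by palbociclib treatment duration, split at the median and at 24 months. The primary-endpoint analysis (SAP 7.1) is a Kaplan-Meier curve with median and 95% CI. OS is "Defined as time from the date of the first dose of the investigational product in J-Ph2 to the date of any-cause death" (SAP 4.1).

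The protocol handles the same information differently. In Table 1 (9.3), "Palbociclib dose modification" has the role of exposure and outcome, not of baseline characteristic, and its source is "J-Ph2 database A5481154 database". Table 2 (9.4.1) continues to collect "Start and Stop date of each dose" and, for palbociclib, "Reason for dose change". The dose-adjustment endpoint in SAP 4.3 has categories (none, one level, two levels, others) but names no database.

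**The concern.** A baseline subgroup must be fixed by the time the survival clock starts. Dose reduction is not. To be counted as reduced, a patient has to live and stay on palbociclib up to the day of the reduction. A patient who dies or stops the drug early has less chance to be reduced and tends to be counted as not reduced. The reduced group cannot have a death before its reduction dates, and the early deaths collect in the other group.

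The results are meant for abstracts and publications (Protocol 12). OS curves by dose reduction, shown beside age and performance status as baseline subgroups, invite the reading that reduction is harmless or even favourable for survival. Timing alone could produce that pattern.

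**Working it through.** **1. Patient flow (Protocol 9.1, SAP 3).** Treated 42, deaths in J-Ph2 8, refused further follow-up 4. 42 − 8 − 4 = 30 under survival follow-up, which matches the documents.

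**2. How many patients are involved.** The number with any dose reduction is not stated. A first reduction recorded only in the new study can occur only among the 30, so it lies between 0 and 30 of 42 (30/42 = 71.4%). The tighter bound is the number still on palbociclib at their last J-Ph2 visit, which the available text does not give. Each such patient is 1/42 = 2.4% of those treated.

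**3. Order of events.** OS starts at first dose. Reduction occurs at some time r > 0 and requires r to be earlier than both death and the end of palbociclib. Group membership is therefore decided by follow-up, not at time 0. For the duration subgroup this is exact: a patient with at least 24 months of palbociclib cannot have died before month 24, so that curve stays at 100% to month 24 by construction.

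**4. Direction and possible size.** The illustration has 400,000 simulated patients per scenario and no effect of reduction on OS. All inputs are assumptions:
- OS exponential, median 60 or 84 months.
- Time on palbociclib exponential, median 24 or 36 months, ended by death if earlier.
- Potential reduction time uniform over the first 12 months for half the patients; for the rest, 12 months plus an exponential time at 0.005 or 0.02 per month.
- J-Ph2 data end at 42 months; follow-up ends at 108 months.

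Kaplan-Meier median OS in months, reduced minus not reduced:

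| OS median | Treatment median | Late rate | J-Ph2 data only | Both databases |
|---|---|---|---|---|
| 60 | 24 | 0.005 | 66.4 − 54.7 = 11.7 | 67.6 − 53.6 = 14.0 |
| 60 | 24 | 0.02 | 68.9 − 50.3 = 18.6 | 70.9 − 47.8 = 23.1 |
| 60 | 36 | 0.005 | 67.2 − 53.7 = 13.5 | 69.4 − 51.4 = 18.0 |
| 60 | 36 | 0.02 | 69.7 − 47.9 = 21.8 | 72.9 − 42.8 = 30.1 |
| 84 | 24 | 0.005 | 90.6 − 78.4 = 12.2 | 92.2 − 76.8 = 15.4 |
| 84 | 24 | 0.02 | 93.0 − 74.5 = 18.5 | 95.3 − 70.8 = 24.5 |
| 84 | 36 | 0.005 | 91.3 − 77.3 = 14.0 | 94.1 − 74.1 = 20.0 |
| 84 | 36 | 0.02 | 93.9 − 71.9 = 22.0 | 97.7 − 64.1 = 33.6 |

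The true difference is zero in every row. The reduced group looks better in all eight, and more so when later reductions are added. Patients first reduced after the J-Ph2 cut number about 0.3 to 1.5 of 42.

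**5. Why a landmark removes it.** Take a landmark L and patients alive at L. In this model, status at L depends only on the potential reduction time and the treatment time up to L. Both are independent of remaining survival, so the expected gap from L onward is zero.

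**The case against.** The strongest reply is that little hangs on this. The study is descriptive with no hypothesis test (Protocol 9.7). SAP 7.4 asks for a median and CI per category, with no hazard ratio or test. The variable is one of ten in the list, and Protocol 9.9 already concedes the small sample and the difficulty of attributing cause. All of that stands and limits the severity. It does not remove the problem, because side-by-side curves are read as a comparison and none of the stated limitations mentions immortal time.

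A reader might go further and infer that the real fault is the single data source: that patients first reduced after J-Ph2 are wrongly counted as not reduced, and that adding the new database would cure it. The documents do not support that.
- SAP 4.4 names one source but defines no categories, so no misclassification can be shown.
- The number of late reducers is unknown and may be zero.
- Table 1 gives sources for dose modification as a study variable, and the protocol lets the SAP modify its plans. A full dose table and a grouping with an earlier cut may legitimately differ.
- Adding later reductions widens the spurious gap in step 4, and under an early landmark these patients are correctly not reduced.

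Nor can one say that every late reducer was on palbociclib on 25 October 2018. That date is the last visit of the last J-Ph2 subject, whereas Protocol Table 3 sets treatment status at each patient's own last J-Ph2 visit.

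**Conclusion.** The point holds as a matter of design. Dose Reduction Group is undefined and post-baseline, and estimating OS from first dose within it favours the reduced group whatever the true effect. The palbociclib-duration subgroup has the same fault.

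The direction follows from the definitions. The size does not: the gaps of 11.7 to 22.0 months (J-Ph2 data) and 14.0 to 33.6 months (both databases) depend on assumed survival, treatment and reduction patterns and are not forecasts for this study. The number of patients affected cannot be derived from the documents. The primary OS estimate is untouched. The change should be made before these subgroup curves are reported, but it is not critical to the study's main result.

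**What to change.** 1. Remove Dose Reduction Group from the list in SAP 4.4. Define its categories by reduction status at a fixed early landmark, for example 6 months after first dose, which should lie within J-Ph2 data.
2. In SAP 7.4, estimate OS from that landmark in patients alive and under follow-up then. State how patients already off palbociclib at the landmark are classified and give their number, since a landmark removes guaranteed time but not confounding.
3. Treat the palbociclib-duration subgroup in the same way, with the landmark at the threshold itself (24 months, or the median duration), because an earlier landmark cannot classify it.
4. For consistency, state that the ever-reduced table in SAP 4.3 uses both databases, as in Protocol Table 1, and that this status is not used to group OS from first dose.

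The cost is SAP wording and a few derived variables, with no new data collection. Patients who die or are censored before a landmark leave that analysis. If the landmark falls before J-Ph2 completion for every patient (an assumption, least certain for the 24-month threshold), the loss is at most the 8 deaths plus 4 refusals, 12/42 = 28.6%, and probably much less at 6 months.

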5 ANALYSIS SET

The analysis set is a population of subjects who were enrolled in J-Ph2 and received the investigational product, excluding surviving subjects who did not give written or oral consent.

6 GENERAL HANDLING

6.1 Statistical Methods

6.1.1 Hypothesis

Not applicable

6.1.2 Descriptive Summary

Continuous variables will be calculated for descriptive statistics (the number of subjects, mean, standard deviation, median, minimum, and maximum), and categorical data will be calculated for the frequency and percentage (%).

Time-to-event data will be calculated for Kaplan-Meier estimates. Data will be plotted using the Kaplan-Meier methods, and as necessary the number of events and censored subjects will be tabulated. The event follow-up period will be estimated based on a reverse Kaplan-Meier method with which the Kaplan-Meier event/censoring indicator variables for the analysis of time to event data are inversely set out.

6.1.3 Confidence interval of time to event

The confidence interval of median time to event will be computed with a Brookmeyer and Crowley method using log-log transformation.

6.2 Day count

In principle, the day of the first dose of the investigational product in J-Ph2 will be defined as Day 1.

6.3 Handling of missing data

6.3.1 Missing dates

If the start or end day of subsequent treatment, the end day of palbociclib, or the end day of letrozole is missing, the “first day” will be imputed. Missing year or month will not be complemented.

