9.6. Data management

Investigators will fill out relevant CRFs based on source documents (eg, patients' medical chart) with a pen, ballpoint pen, etc. After the completion of CRFs, the investigator will promptly submit them to the sponsor by mail.

When receiving a query from the sponsor on the completed CRF (ie, Data Clarification Form [DCF]), investigators will reconfirm the information on source documents, fill out the DCF as required, and submit the DCF to the sponsor.

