3 STUDY DESIGN

This is a Japanese, multicenter, retrospective, observation study. This observation study is designed as a follow-up study to the Japanese phase 2 study of palbociclib (NCT01684215, the phase 2 part of Study A5481010; hereinafter, J-Ph2). In J-Ph2, 43 subjects were enrolled and 42 received palbociclib plus letrozole. Eight deaths were reported at the end of J-Ph2 (i.e., last subject last visit [LSLV], October 25, 2018). Of the remaining 34 subjects with no reported deaths, 4 refused further follow-up and 30 were being followed up for survival.

Medical charts of those 30 subjects in the post-J-Ph2 survival period will be used to retrospectively collect OS and subsequent-treatment data. For subjects transferred to another hospital, the investigator will be requested to make his/her utmost efforts to collect data from the hospitals to which the subjects were transferred. The investigator will complete paper-based case report forms (CRFs) at the start of the study at each site and during the annual reporting period specified by the sponsor. Subject IDs assigned in J-Ph2 will be used to collate the subject demographics and other relevant data between this observation study and J-Ph2 and to analyze the data.

Eight subjects with OS events confirmed in J-Ph2 and 4 who refused to continue follow-up after J-Ph2 will be analyzed based on data collected in J-Ph2.

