4.2 Secondary Endpoints

Overview of Subsequent Treatment

Subsequent treatment subject to data collection will be limited to systemic therapies prescribed by physicians for advanced breast cancer (chemotherapies, hormone therapies, molecular targeted drugs, etc.).

- Percentage of subjects by types of subsequent treatment (category: endocrine therapy-based, chemotherapy-based, others)
- Percentage of subjects by treatment line (category: no subsequent treatment, first subsequent treatment, second subsequent treatment)

Subsequent-treatment period

Defined as time from the start date to the end date of each line of treatment among subjects who received subsequent treatment. If "Ongoing" is checked for the latest record of an applicable subsequent treatment, data will be cut off at the date on which the CRF with "Ongoing" is fixed.

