7.2 Secondary Endpoints

Percentage of subjects receiving subsequent treatment

The number and percentage of subjects will be calculated for treatment lines (First, Second) and types of subsequent treatment. Changes in subsequent treatment in subjects who proceeded to receive subsequent treatment will be summarized and plotted on graphs.

Subsequent-treatment period

Data for each treatment line will be summarized using a Kaplan-Meier method and plotted on graphs. The duration of subsequent-treatment period for each treatment line will be estimated for median and 95%CI. The same analyses will be performed for each type of subsequent treatment per treatment line.

The duration of all subsequent treatment will be plotted for each subject.

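### SAP 6.3.1 sets no floor for an imputed end day, so a subsequent therapy that starts and stops in the same month can get a negative duration (minor)

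*SAP*

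**What the plan says.** SAP 6.3.1 is the only rule for partial treatment dates. It applies "If the start or end day of subsequent treatment, the end day of palbociclib, or the end day of letrozole is missing", and the value imputed is the first day. A missing month or year is left missing, so the first day is read here as day 1 of the recorded month. The section sets no condition that links the imputed date to the other date of the same therapy.

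The imputed dates feed these analyses:

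- SAP 4.2, subsequent-treatment period: "Defined as time from the start date to the end date of each line of treatment among subjects who received subsequent treatment".
- SAP 7.2: "Data for each treatment line will be summarized using a Kaplan-Meier method and plotted on graphs", with a median and 95% CI, repeated by treatment type within line, and with a per-patient plot of all durations.
- SAP 4.3, palbociclib duration per dose: it "is defined as time from the date of the first dose to the end of treatment with the dose level". SAP 7.3 only plots it.

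SAP 6.2 fixes Day 1 as the first dose in J-Ph2 but does not say how the length of a later line is counted. Protocol 9.4, 9.7.3 and 9.7.4 add no floor, no minimum duration and no rule for an end date that precedes a start date.

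**The concern.** If a line starts after day 1 and stops later in the same month, and only its stop day is unknown, the rule moves the stop to before the start. The result is an impossible duration produced by following the SAP exactly. A negative time is not valid in Kaplan-Meier and cannot be drawn as a bar. The SAP does not say whether to keep it, set it to 0 or drop it, so two programmers could report different results from the same data.

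Duration of subsequent therapy is part of the secondary objective. The lines affected are those stopped within a month, which form the early part of the curve. Partial dates are foreseeable: data come from charts, some held at other hospitals, and Protocol 9.9 lists incomplete data as a limitation.

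**Working it through.** The plan states no figure that can be reproduced on this point. The check has a date-arithmetic part, which needs only the rule, and a frequency part, which needs assumptions.

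**1. Date arithmetic.** Let s be the known start day, with the stop on an unknown day of the same month. The imputed stop is day 1.

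- End minus start: duration = 1 - s. This is negative for every s above 1.
- With one day added: duration = 2 - s. This is negative for every s above 2.
- Example: start on day 10, true stop on day 24. The true duration is 24 - 10 = 14 days (15 inclusive). The rule gives 1 - 10 = -9 (or -8).
- In a 30-day month, 29 of 30 start days give a negative value (28 of 30 with one day added). The lowest value is -29 (-28).

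Cases in which a negative value cannot arise:

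- Both days missing in one month: both become day 1, so the duration is 0 (1 inclusive).
- Only the start day missing: it moves to day 1, so it is never after the stop.
- Stop in a later month: the shortest case is 31 March to 1 April, which is 1 day.

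**2. How often.** The documents give no missing rate, number of lines or duration. Assumed: 30 uncensored lines; start dates uniform over 2019-2022; exponential or gamma (shape 2) durations; start and end days missing independently, each at 10%, 20% or 30%. The share p of negative lines was simulated, and the chance of at least one in 30 lines is 1 - (1 - p)^30.

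At a 90-day median, p is 0.96%, 1.63% and 2.15% (exponential) or 0.34%, 0.60% and 0.77% (gamma). For example, 1 - (1 - 0.0163)^30 = 39%, and 1 - (1 - 0.0060)^30 = 17%.

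| Assumed true median | Exponential, 10% to 30% missing | Gamma, 10% to 30% missing |
|---|---|---|
| 90 days | 25% to 48% | 10% to 21% |
| 180 days | 13% to 29% | 3% to 7% |
| 365 days | 7% to 15% | 1% to 2% |
| Any, both days always missing together | 0% | 0% |

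**3. Effect on the median.** This used 40,000 samples of 30 lines in each of 12 scenarios (2 shapes, end-only or independent gaps, 3 rates), or 480,000 samples, at a 90-day median.

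- Negative values kept or set to 0: the median was identical in all samples, because these records rank lowest either way.
- Negative values dropped: in affected samples the median rose by about 5 to 7 days (exponential) or 3 days (gamma). The sampling SD was about 24 days (exponential) or 15 to 16 days (gamma).

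**4. After a floor.** If the imputed stop is the later of day 1 and the start date, the same-month duration is 0 days (1 inclusive) for every s. No negative value remains.

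**The case against.** The strongest reply is that this is a rare case with almost no effect. Protocol 9.9 ties incomplete data to transferred and deceased patients, and for them both dates of a line plausibly come from the same poor source. Gaps would then tend to occur together, and the chance of a negative time falls towards 0%. The 90-day exponential case is also the least favourable shown. Both points stand, which is why the table gives the full range and no single figure.

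A second reply is that an error would be seen. Under Protocol 9.6, on a query "investigators will reconfirm the information on source documents"; Protocol 9.8 adds remote monitoring, and each duration is plotted per patient. This stands for detection. It gives no rule for a day that is still unknown after the query.

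A reader might infer something stronger: that first-day imputation materially biases treatment durations. The documents do not support that. For subsequent therapy the average error is about -14.7 days with only the end day missing and +14.7 days with only the start day missing. These cancel if the two gaps are equally common, and nothing in the documents says otherwise. For palbociclib and letrozole the rule covers end days only, so the shift is always towards shorter. But SAP 7.4 uses palbociclib duration only to form subgroups ("for each category of the duration of palbociclib treatment (threshold: median, 24 months"). With assumed median treatment of 18 to 30 months and 10% to 30% of end days missing, 0.03 to 0.13 of 42 patients would cross 24 months. Even that applies the missing rate to everyone, although some end dates are J-Ph2 trial data. Per-dose palbociclib duration is plotted and does not enter Kaplan-Meier, so its consequence is smaller still.

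**Conclusion.** Minor, but wrong as written: a stated rule yields an impossible value in a Kaplan-Meier analysis of a secondary endpoint. The date arithmetic needs no assumption beyond reading the first day as day 1 of the recorded month.

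How often it will occur cannot be known from the documents; the chances above rest on assumed missing rates, durations, number of lines and pattern of gaps. Whichever way a negative record is handled, the median moves by an amount well within sampling error. Overall survival in the whole analysis set is untouched, because the rule does not cover the date of death or the date last known alive. The study is descriptive, with no hypothesis test. The reason to act is that the handling would otherwise be chosen after the data are seen.

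**What to change.** Add to SAP 6.3.1 that an imputed end date is the later of the first day of the recorded month and the known start date of that therapy. For the last palbociclib dose level, the bound is the recorded start of that level. Also report the number of imputed dates. A different imputed day, such as mid-month, is not needed to remove negative times.

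The cost is one or two sentences and a short programming change. No new data are needed. The CRF already records "Start and Stop date of subsequent therapy" and the start of each palbociclib dose (Protocol 9.4.1). The 8 deaths and 4 refusals "will be analyzed based on data collected in J-Ph2".

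The downside is that a few lines get a duration of 0 days (1 if counted inclusively), which Kaplan-Meier can use. At an assumed 90-day median this is about 4% (gamma) to 11% (exponential) of the records with only the end day missing. The floor does not remove the average shortening of those records, which stays at about 13 to 15 days each.

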9.9. Limitations of the research methods

Limitations of the research method in this study include;

1. Single-arm design. Since no control group is set in the study, there is a limitation on interpretation on results, especially time-to-event endpoints.
2. Observational, retrospective design. Since this study collects data basically from medical charts of each patient, there is a potential for missing, inaccurate, or incomplete data. If the patients had been transferred to another hospital or had already passed away, data in these patients may not be fully collected or be missing information in this study. In addition, considering the observational nature, there is methodological challenges in attributing causality to outcomes.
3. Small sample size. It may be difficult to draw definitive conclusion due to lack of power.

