7.1.2 Sensitivity analysis/supportive analysis for the primary endpoint

Not applicable

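### SAP 6.3.1 sets a missing start day and a missing end day alike to the first of the month, which shifts a line lacking only one of them by 14.7 days on average and can place an end before its start

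*SAP*

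**What the plan says.** SAP 6.3.1 covers four dates with a single rule: "If the start or end day of subsequent treatment, the end day of palbociclib, or the end day of letrozole is missing", the first day is imputed. It then adds: "Missing year or month will not be complemented". Since only the day is filled in, and month and year must be known, the one workable reading is day 1 of the recorded month.

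The dates feed these planned outputs:

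- **Subsequent-treatment period (secondary endpoint).** SAP 4.2: "Defined as time from the start date to the end date of each line of treatment among subjects who received subsequent treatment". SAP 7.2: "The duration of subsequent-treatment period for each treatment line will be estimated for median and 95%CI", and again by type of therapy within each line.
- **Time to start of chemotherapy.** SAP 4.3 runs this from the first J-Ph2 dose to the first subsequent chemotherapy or death.
- **Palbociclib and letrozole durations.** SAP 4.3 and 7.3 plot them per patient. SAP 7.4 also uses palbociclib duration, cut at its median and at 24 months, to form OS subgroups.

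For a line still running, SAP 4.2 states: "data will be cut off at the date on which the CRF with 'Ongoing' is fixed". Such a line has no end day to impute.

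Neither document bounds an imputed date by the patient's other dates, and neither plans a sensitivity analysis for imputed dates.

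**The concern.** Day 1 is neutral for neither end of an interval. As an end date it can only understate the duration, and as a start date it can only overstate it; the error is zero only when the true day is the 1st. For palbociclib and letrozole the rule covers only the end day, so nothing offsets the shortening, and a patient just above the 24-month cut-off can fall into the shorter-duration OS subgroup.

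The rule can also produce an impossible record. A line that starts on a known 20 March and is recorded as ending in March gets an end date of 1 March, 19 days before it began. An imputed start can likewise precede the known stop of the previous line. The SAP does not say what to do in either case.

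Partial dates are foreseeable in chart data. Protocol 9.9 says that "there is a potential for missing, inaccurate, or incomplete data", and adds: "If the patients had been transferred to another hospital or had already passed away, data in these patients may not be fully collected".

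**Working it through.** The documents give no figure on this point, so there is nothing to reproduce first.

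**Inputs.** From SAP 6.3.1: day 1 is imputed, with month and year known. Assumed: the true day is uniform within its month. Assumed for the effect on lines and medians: exponential line durations with medians of 3, 6, 9 or 12 months (1 month = 30.4375 days). The documents give neither line durations nor a rate of missing days.

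**1. Error in one date.** Error = imputed day minus true day. For a month of L days the mean is -(L - 1)/2: -13.5 (28 days), -14.0 (29), -14.5 (30), -15.0 (31).

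Over a 365-day year, the sum of (day - 1) is 378 + 4 × 435 + 7 × 465 = 5,373, and 5,373/365 = 14.7 days. The sum of squares is 6,930 + 4 × 8,555 + 7 × 9,455 = 107,335, so the root mean square error is √(107,335/365) = 17.1 days.

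For day 15 the mean error is 14 - 14.7 = -0.7 day.

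| Imputed day | Mean error (days) | RMSE (days) | Largest error (days) |
|---|---|---|---|
| 1st | -14.7 | 17.1 | 30 |
| 15th | -0.7 | 8.8 | 16 |

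**2. Error in one line.** Duration is end minus start.

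- End day only missing: -14.7 days on average.
- Start day only missing: +14.7 days on average.
- Both missing: the two terms offset on average.

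A simulation of 400,000 lines at each assumed median agrees: -14.7, +14.7 and between -0.04 and -0.07 day.

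**3. Relative size and impossible dates.** The relative size is 14.7/(median × 30.4375). The last column is the simulated share of lines lacking only the end day whose imputed end falls before the known start.

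| Assumed median (months) | 14.7 days as % of median | End before start |
|---|---|---|
| 3 | 16% | 10% |
| 6 | 8% | 5% |
| 9 | 5% | 3% |
| 12 | 4% | 3% |

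**4. Effect on a reported median.** If a fraction of lines lacks only the end day and all others are complete, the simulated median falls as follows, across the four assumed medians.

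| Fraction lacking only the end day | Fall in median (days) |
|---|---|
| 10% | 1 to 2 |
| 20% | 2 to 3 |
| 30% | 4 to 5 |
| 50% | 7 |

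**5. Scale against sampling error.** Take the most favourable case for precision: all 42 treated patients contribute an uncensored line, with a 6-month median (182.6 days). The standard error of the log median is 1/(ln 2 × √42) = 0.223. The approximate 95% interval is 182.6 × exp(±1.96 × 0.223), about 118 to 283 days.

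**The case against.** The strongest reply is that the rule is pre-specified, explicit and reproducible, and that its effect on any reported figure is not shown to matter. Much of this stands.

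- **Overall survival.** A reader might infer that the primary result is biased. It is not: the rule does not reach death or last-alive dates, which define OS. The only route to OS is membership of the palbociclib-duration subgroups.
- **Size.** A reader might take the percentages in step 3 as the bias in the reported medians. They describe one affected line. The median moves by about 1 to 7 days in the scenarios of step 4, against an interval some 165 days wide (283 - 118) in step 5. The study is also descriptive, with no hypothesis test.
- **Pattern of gaps.** A reader might infer that transferred patients mostly lack the end day alone. Protocol 9.9 says only that their data may be incomplete. Both days could be missing, and then the errors offset on average. Protocol 9.1 asks investigators to obtain data from the receiving hospital, and 9.6 and 9.8 provide queries and remote monitoring to resolve gaps.
- **Study drugs.** By Protocol Table 3, only patients still on treatment at their last J-Ph2 visit need the discontinuation form here. Treatment durations are plotted per patient, with no median planned.
- **Time to chemotherapy.** The 75% one-year PFS cited in Protocol section 7 suggests times above 12 months, where 14.7 days is 4% or less of an affected record (14.7/365.25 = 4.0%).

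These points limit the weight of the concern. They do not make day 1 a neutral value for an end date, and they do not supply the missing rule for an end that precedes its start.

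**Conclusion.** The point holds as a minor defect. Under the stated rule a line lacking only its end day is shortened by 14.7 days on average, and one lacking only its start day is lengthened by as much (range 0 to 30 each). Time to chemotherapy can only be brought forward, and palbociclib and letrozole durations can only shrink. The direction follows from the rule alone; the size rests on true days being uniform within the month.

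The net bias in a line's median depends on an unknown mix of start-only, end-only and double gaps, so neither its sign nor its size can be stated from the documents. The 1 to 7 days applies to end-only gaps in 10% to 50% of lines with exponential durations. If few days are missing, the effect is close to nil.

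The firmest part needs no assumption about rates: the rule can produce an end date before a known start, and the SAP has no provision for it.

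**What to change.** In SAP 6.3.1, impute day 15 for a missing start or end day when month and year are known. Constrain the result to the patient's known neighbouring dates: the line's own start or stop, the previous stop, the next start, and death or last-alive date. Report the number of imputed dates.

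The bounding is needed with day 15 too. In the 20 March example an unbounded day 15 would still precede the start; bounded, it becomes 20 March.

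The cost is a short SAP revision and a few lines of bounding code. The price in accuracy is a small residual error: a mean of about -0.7 day and at most 16 days before bounding, against -14.7 and 30 under the present rule.
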